8.5.3 Corrective and preventative actions and principal investigator disqualification criteria

Protocol deviations and site/PI non-compliance will be closely monitored by the ARC and appointed study personnel. Identifying deviations and taking corrective actions at the earliest possible stage increases the potential for clinical trial success and reduces patient risk. The initiation of a corrective and preventative action (CAPA) to investigate and establish corrective actions may be required in some cases. The ARC reserves the right to close a clinical study site or replace a PI if non-compliance is observed.

8.6 Audits and inspections

In the event that an Investigator is contacted by a Regulatory Agency in relation to this trial, the Investigator will notify the ARC immediately. The Investigator and study site research personnel must be available to respond to reasonable requests and inspection queries made during the inspection process. The Investigator must provide the ARC with copies of all correspondence that may affect the review of this trial. The ARC will provide any needed assistance in response to regulatory inspections.

9. STUDY MANAGEMENT

9.1 Training

9.1.1 Training of Monitors

The ARC's monitors or designee will be trained to the protocol, randomization instructions, electronic case report forms, and study drug usage. The ARC or designee is responsible for the training. Training will be conducted in accordance with the ARC's and/or designee's standard procedures.

9.1.2 Training of study site research personnel

Participating investigators and study site research personnel will be trained during site initiation visits conducted by the Mount Sinai Clinical Coordinating Center or designee.

All training must be documented and must include or reference the revision of materials used for training, who was trained, the trainer and date of training. Original training records should be maintained at the site in the Regulatory Binder and copies should be dispensed to Mount Sinai Clinical Coordinating Center.

Site initiation/training involves a didactic session whereby the protocol, including screening procedures, clinical follow-up procedures, and study drug procedures are reviewed in detail along with investigator responsibilities.

In addition, the Mount Sinai Clinical Coordinating Center will assure that all participating investigators and study personnel are trained in the following:

- Protocol requirements, including patient screening requirements, inclusion/exclusion criteria, procedural requirements and subject follow-up requirements
- Study and personnel requirements
- Informed consent requirements
- Adverse event reporting
- Drug accountability procedures
- Electronic CRF completion
- Regulatory binder maintenance.

9.2 Monitoring of the study

The ARC and/or designee will monitor the trial over its duration according to the pre-specified monitoring plan. The trial monitor will contact each site at appropriate intervals to review investigational data for accuracy and completeness and ensure compliance with the

clinical investigation plan. The trial monitor may request all documents and required records that are maintained by the Investigator/Site, including medical records (office, clinic, or hospital) for the subjects in this trial. Source documentation must be available to substantiate proper informed consent procedures, adherence to protocol procedures, adequate reporting and follow-up of adverse events, accuracy of data collected on case report forms, and study drug information. The Investigator and/or study site research personnel will be available for monitoring contact. If a site visit is required, it is expected that the Investigator/Site will provide the trial monitor with a suitable working environment for review of study-related documents.

9.2.1 Source data

The Investigator is responsible for maintaining complete and accurate documentation of the trial including but not limited to medical records, trial progress records, laboratory results, case report forms, signed informed consent forms, study drug accountability records, correspondence with the IRB/EC, the trial monitors, and the ARC, as well as adverse event reports and information regarding subject discontinuations.

The Investigator is required to maintain information in the subject's medical records which documents and corroborates data entered in the case report forms. As a minimum the subject record should contain:

- Medical history/physical exam documenting that subject meets inclusion/exclusion criteria
- Documentation of subject's consent and subject ID number in the trial
- Dated and signed notes from each subject visit
- Adverse events reported and their resolution or lack thereof including supporting documents such as hospital records, discharge summaries, catheterization reports, and ECGs.
- Record of protocol required medications during the trial
- Record of the subject's condition upon completion of or withdrawal from the trial

The Investigator and the associated institution will permit direct access to source data/documents for study-related monitoring, audits, IRB/EC review, and regulatory inspections.

Subjects providing informed consent agree to allow the ARC or designee access and copying rights to pertinent information in their medical records concerning their participation in this trial. The Investigator will obtain, as part of the informed consent, permission for trial monitors or regulatory authorities to review, in confidence, any records identifying the

subjects in this trial. This information may be shared with regulatory agencies; however, the ARC undertakes not to otherwise release the patient's personal and private information.

9.3 Study timetable and end of study

The trial is estimated to commence February 1st, 2015. The last subject follow-up at 18 months post-procedure is expected to occur in February 2018. The total expected duration of the trial is 36 months.

10. DATA MANAGEMENT

A computerized data entry and management system will be developed during the initial project months by an independent academic research center. A closed and password protected data entry system has been designed to ensure that only the responsible data entry person and the Data Management site supervisor can enter and/or edit data and this can be done only by using the programs and/or utilities available on the menu system. An audit trail will be created by date/time and user stamping. Range checks, review screens, and various error trapping routines are built into the system as quality control procedures. All possible relevant information on the forms is pre-coded. Specific instructions and explanation of choices will be provided for all data forms.

The statistical programmer will perform additional data checks, data cleaning, and variable coding to create analysis datasets using SAS. The programmer will also create a reporting system that generates study specific tables, listings, and figures, which will be run periodically to monitor study and data entry. As a final check on data integrity, the Director of Clinical Biometrics and study biostatistician will check these outputs against the raw data in order to resolve any discrepancies. The Biometrics lead, statistician, and statistical programmer will be responsible for working with the project staff to ensure the integrity of the data entry process.

11. EVALUATION AND CALCULATION OF VARIABLES

11.1.1 Primary Bleeding Endpoint

The primary bleeding endpoint of the present study is the time to first occurrence of clinically relevant bleeding, defined as Bleeding Academic Research Consortium (BARC) Types 2, 3 or 5 bleeding.

11.1.2 Secondary Bleeding Endpoints

Time to first occurrence of:

- Types 3 or 5 bleeding according to definitions from BARC
- Minor or major bleeding according to definitions from Thrombolysis in Myocardial Infarction (TIMI)

- Moderate or severe or life-threatening bleeding according to definitions from GUSTO
- Major bleeding according to definitions from International Society of Thrombosis or Hemostasis (ISTH)

11.1.3 Primary Ischemic Endpoint

The primary ischemic endpoint of the present study is the time to first occurrence of confirmed all-cause death, non-fatal myocardial infarction, or stroke.

11.1.4 Secondary Ischemic Endpoints

Time to first occurrence of:

- cardiovascular death, non-fatal myocardial infarction, ischemic stroke or clinically-driven revascularization
- cardiovascular death, non-fatal myocardial infarction or ischemic stroke
- definite or probable stent thrombosis
- cardiovascular death
- non-fatal myocardial infarction
- cardiovascular death, non-fatal myocardial infarction or definite or probable stent thrombosis
- ischemic stroke
- all-cause mortality

12. STATISTICAL METHODS AND SAMPLE SIZE DETERMINATION

The statistical analyses will be performed using SAS version 9.0 or greater and Stata versions 12.0 or greater.

12.1 Description of analysis sets

The Enrolled Population consists of all subjects who signed informed consent.

The intention-to-treat (ITT) population will consist of all subjects who have been randomized (i.e. when the subject number and allocated treatment are recorded in the EDC). Subjects will be analyzed in the treatment group assigned by the EDC.

The per-protocol population (PP) will consist of all randomized subjects without any major deviations from the protocol. The following deviations will lead to exclusion from the PP population

- Subjects not receiving the assigned treatment as allocated by the EDC or no treatment at all
- Non-compliance to study drug (aspirin or placebo) or ticagrelor. Non-compliance is defined as taking less than 80% of dispensed tablets based on manual pill bottle count at each study visit.

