5.8 Discontinuation of investigational product or study drug

Study-provided medications (open-label ticagrelor or blinded study drug) may require *temporary interruption* for the following reasons:

- 1. Surgery or invasive procedure:** Study-provided medications should be resumed after surgery once the risk of bleeding is no longer considered prohibitive in the judgment of the treating physician. Minor surgeries and procedures, including but not limited to tooth extraction, colonoscopy and endoscopy, may be safely performed on low-dose aspirin and therefore do not require temporary interruption of blinded study drug. However, if deemed necessary and at the discretion of the treating physician, open-label ASA may be substituted for blinded study drug in the peri-operative period. Blinded study drug may then be restarted at the discretion of the treating physician after completing the mandatory course of open-label ASA.
- 2. Balloon angioplasty or PCI with bare-metal stent:** In the event of coronary revascularization with balloon angioplasty alone or PCI with bare metal stent, blinded study drug may be temporarily interrupted for 2-4 weeks while patients receive open-label ASA at the discretion of the treating physician in accordance with local practice and standard of care. Blinded study drug may then be restarted at the discretion of the treating physician after completing the mandatory course of open-label ASA.
- 3. Clinically Significant Bleeding:** Study-provided medications should be temporarily interrupted pending resolution of the acute bleeding episode and

may be restarted at the discretion of the treating physician if deemed clinically safe and in accordance with local practice and standard of care.

4. Details surrounding the date, duration and reason for each episode of temporary interruption should be entered in the appropriate section of the EDC.

Study-provided medications (open-label ticagrelor or blinded study drug) may require *permanent discontinuation* for the following reasons:

1. Patient decision: The patient is at any time free to discontinue treatment, without prejudice to further treatment.
2. Investigator's decision:
 - a. Incorrectly enrolled patient in whom the inclusion/exclusion criteria violation would put the patient at undue risk

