 - b. Adverse Events felt to be related to either study medication for which Investigator feels continued treatment would put the patient at undue risk, such as severe or life-threatening bleeding, myocardial infarction, stent thrombosis, ischemic stroke or coronary revascularization with a DES.
3. Renal failure requiring dialysis
4. Chronic oral anticoagulation
5. Details surrounding the date, duration and reason for permanent discontinuation of study medication should be entered in the appropriate section of the EDC.
6. In the event of permanent discontinuation of either study medication, further antiplatelet therapy is at the discretion of and is to be provided by the patient's treating physician. Any remaining study-provided medication should be returned to the local site at the next scheduled follow-up visit. Although these patients will no longer receive study-related medication, follow-up will continue in all randomized patients until end of study

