8.5.2 Procedures for recording, reporting, and analyzing protocol deviations

A deviation is an instance(s) of failure to follow, intentionally or unintentionally, the requirements of the protocol. All deviations must be reported to the ARC. The occurrence of clinical investigational plan deviations will be monitored by the ARC or designee. It is the Investigator's responsibility to inform their IRB/EC of clinical investigational plan deviations in accordance with their specific IRB/EC reporting policies and procedures.

In the event that an investigative site does not comply with the Investigator Agreement or clinical investigational plan, the ARC will notify the Investigator of the site's non-compliance. Continued non-compliance may result in further escalation in accordance with the ARC's standard procedures.

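### The 80%-of-tablets rule for the per-protocol set does not exempt tablets left untaken after a primary ischemic event, so an endpoint can remove its own patient from the set that decides non-inferiority

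*Combined protocol and SAP*

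**What the plan says.** Section 12.1 lists deviations that lead to exclusion from PP. One is non-compliance with blinded study drug or ticagrelor: "Non-compliance is defined as taking less than 80% of dispensed tablets based on manual pill bottle count at each study visit". The denominator is tablets dispensed, not tablets due up to an event or a permitted stop.

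Section 5.8 allows permanent discontinuation by investigator decision for "Adverse Events felt to be related to either study medication for which Investigator feels continued treatment would put the patient at undue risk". Its examples are "severe or life-threatening bleeding, myocardial infarction, stent thrombosis, ischemic stroke or coronary revascularization with a DES". MI and stroke are components of the primary ischemic endpoint (11.1.3). After a permanent stop, "Any remaining study-provided medication should be returned to the local site at the next scheduled follow-up visit", and follow-up continues to the end of the study.

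Drug is supplied for six months at randomization (5.2.1). A second supply is given at month 9 only to patients still on drug (6.2.3). Pill counts are made at months 9 and 15 (5.7).

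Sections 12.1.2 and 12.2 place the ischemic non-inferiority decision in PP: the upper 95% limit of the absolute risk difference must not exceed 1.6%. ITT is a secondary analysis of the same endpoint, and 12.2 does not tie it to the margin.

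**The concern.** Exclusion from the deciding set can be a consequence of the outcome. A patient who has an MI two months after randomization, stops drug and returns the rest has taken about a third of the first supply. As 12.1 is written, that patient and the MI leave PP.

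The margin is absolute and fixed. Thinning events in both arms by the same proportion lowers both risks and the difference between them, while the margin stays at 1.6 points. A truly inferior regimen could then pass more often than 2.5% of the time, even with intact blinding and equal stopping by arm.

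Two gaps add to this. Section 12.1 does not say how a patient who dies before a pill count is classed. It also does not say whether 80% must be met at every visit, at any visit or cumulatively, so two statisticians could build different PP sets from the same data.

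**Working it through.** **The plan's own figure.** With 8.0% in both arms, 4100 per arm (1:1 assumed) and one-sided 0.025, SE = √(2 × 0.08 × 0.92/4100) = 0.00599. Power = Φ(0.016/0.00599 − 1.96) = 76.1%, against the stated 80%. That gap is a separate matter and nothing below depends on it.

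**Who falls below 80%.** Assume 180 daily tablets per six-month supply, so the threshold is 144.
- Stop on day 60: 60/180 = 33%.
- For stops spread evenly over 360 days with full compliance until then, the share of stoppers removed depends on the reading:
  - failing any visit: (144 + 144)/360 = 80%
  - cumulative count: (144 + 108)/360 = 70%
  - failing every visit: 144/360 = 40%

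**Effect on PP risk.** Let f be the share of event patients removed by event-driven stops (stop fraction × share above), b₁ the background exclusion in event patients and b₀ the exclusion in event-free patients. Then

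p′ = p(1−b₁)(1−f) / [p(1−b₁)(1−f) + (1−p)(1−b₀)].

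True risks are set at the margin, 8.0% vs 9.6%. With b₁ = b₀ the formula reduces to p(1−f)/(1−pf):
- 10% stop, any-visit reading, f = 0.08: 7.41% vs 8.90%, difference 1.49 points.
- 25% stop, any-visit reading, f = 0.20: 6.50% vs 7.83%, difference 1.33 points.

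**Chance of declaring non-inferiority.** Simulated with 1,000,000 runs, unpooled Wald upper limit ≤ 1.6%, b₁ = b₀ = 4%, equal stopping by arm. Ranges run over the three readings.

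| Event patients who stop | Deaths removable | Deaths 20-40% of events, kept in PP |
|---|---|---|
| 0% | 2.5% | 2.5% |
| 10% | 3.1-3.8% | 2.8-3.5% |
| 25% | 4.1-6.9% | 3.4-5.5% |

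ITT stays at 2.5% throughout.

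**Sensitivity to event-free exclusion.** Keep 10% stopping, the any-visit reading and b₁ = 4%, and raise b₀:
- b₀ = 10%: 7.86% vs 9.44%, difference 1.58 points, false non-inferiority about 2.8%.
- b₀ = 15%: 8.29% vs 9.94%, difference 1.65 points, about 2.1%.

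The sign changes where b₀ equals total event-patient exclusion, 1 − 0.96 × 0.92 = 11.7%.

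**Sensitivity to imbalance** (b₁ = b₀ = 4%, deaths removable). Stopping of 12% in control and 8% in the experimental arm gives 1.4-1.9%; the reverse gives 4.8-8.7%.

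**The case against.** **A permitted stop is not a deviation.** Section 12.1 speaks of major deviations, and section 8.5.2 says "A deviation is an instance(s) of failure to follow, intentionally or unintentionally, the requirements of the protocol". A stop that 5.8 allows is arguably no such failure. That reading is available, but 12.1 defines non-compliance numerically and lists it among deviations that lead to exclusion. The general definition does not override the specific rule.

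**The trigger is narrow.** A reader might infer that every MI or stroke ends treatment and removes the patient. The documents do not say so. Section 5.8 requires suspected relation to study medication and a judgement of undue risk. A late stop within a supply window can still pass 80%. A death produces no stop decision, and without a pill count it does not clearly meet the exclusion, so the rows with deaths kept are at least as natural. This stands and limits the claim to some patients.

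**The inputs are assumed.** No stop fraction is given. The 4% appears in 12.3 only as non-compliance/cross-over for the bleeding sample size, not as a PP exclusion rate. Event-free patients may stop for bleeding, other adverse events or by choice, so higher event-free exclusion is plausible. This also stands. Blinding of aspirin/placebo makes a large imbalance by arm less likely, so the 8.7% figure is a stress case.

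**ITT is already planned.** It keeps these events because follow-up continues, and a discrepancy would be visible. But it does not decide the test, and no rule covers disagreement between the two sets.

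**Conclusion.** The defect is real and structural: as written, the PP rule can remove patients because they had the primary ischemic endpoint, from the only set on which the 1.6% criterion is judged.

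A reader might go further and conclude that the plan inflates the type I error of the non-inferiority test. The documents do not support that. The test is anti-conservative if event patients are excluded more often than event-free patients, equally by arm. With higher event-free exclusion, or unequal stopping, the bias can vanish or run the other way. Neither size nor direction can be fixed from the documents.

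The illustrations of about 2.8-3.8% (10% stopping) and 3.4-6.9% (25% stopping) rest on 1:1 allocation, 180-tablet supplies, evenly spread stops, full compliance until the stop and 4% exclusion in both groups. They show that the effect need not be trivial; they do not predict it.

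**What to change.** In 12.1, state that:
- tablets not taken after a first primary ischemic event are not non-compliance, and the event is counted in PP;
- compliance for such a patient is judged only up to the event or the recorded stop date, using tablets dispensed minus tablets returned;
- a patient who continues drug after the event has no count at the event date, so the ordinary visit count is used with recorded post-event interruption days removed;
- a patient who dies before a pill count is not excluded for lack of one;
- the 80% threshold applies per visit or cumulatively, with one reading chosen.

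Other discontinuations should not be exempted, since 5.8 says "The patient is at any time free to discontinue treatment, without prejudice to further treatment" and a general exemption would empty the PP definition.

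In 12.1.2 and 12.2, state that the ITT risk difference is reported against the same 1.6% margin beside the PP result. ITT keeps all events and is free of this selection.

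**Cost.** This is a protocol amendment under 8.4, plus programming. No new data are needed: "Details surrounding the date, duration and reason for permanent discontinuation of study medication should be entered" in the EDC, likewise "Details surrounding the date, duration and reason for each episode of temporary interruption should be entered", and tablets are returned. The PP result may be less favourable. Unrecorded lapses after an event could still exclude a patient who continues drug.

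An asymmetry also remains, because event patients have less time to fail the 80% rule than event-free patients. This tends to be conservative. With 10% event-free and 5% event-patient exclusion, false non-inferiority is about 2.0%, and power at equal 8.0% rates is about 69.9%, against 71.6% with 10% in both groups. The change should therefore not be described as restoring exactly 2.5%.

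Requiring both sets to meet the margin is an optional design choice. At 4% exclusion it lowers power from about 74.4% to 72.7%.

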5.2 Subject randomization and initiation of investigational product

5.2.1 Procedures for randomization

The eligibility for randomization for all enrolled subjects will be evaluated at the in-person 3-month study visit. Subjects with any of the following will not be randomized:

- Refusal of randomization by subject or treating physician
- Withdrawal of consent
- Lost to follow-up
- Death
- Major bleeding (BARC Types 3b or greater)
- Occurrence of an ischemic event after PCI such as myocardial infarction, definite or probable stent thrombosis, ischemic stroke, coronary revascularization with drug-eluting stent
- No longer taking DAPT with aspirin and ticagrelor
- Non physician-guided cessation of aspirin or ticagrelor of 5 consecutive days or greater.
- Women of child bearing potential (as defined in Section 4.2)
- Renal failure requiring dialysis
- Current indication for oral anticoagulation or high dose aspirin

Randomization will be performed within the EDC system among subjects eligible for randomization. The EDC will allocate the treatment group assignment for the subject and provide study site research personnel the appropriate bottle ID number(s).

Upon randomization at the conclusion of the in-person 3-month visit, the study site research personnel will provide a 6-month supply of blinded investigational product (aspirin or matching placebo) and open-label ticagrelor.

Enrolled subjects who do not meet eligibility for randomization will have completed their protocol required activities and therefore will not receive any further study-provided medications. Their treating physician will also be notified that the patient's protocol-mandated study activities have concluded. Further antiplatelet therapy will be at the discretion of the subject's treating physician in accordance with local standard of care. Vital status of these subjects will be determined at the 18-month time point.

Enrolled subjects who do not meet eligibility for randomization *prior to* the in-person 3-month visit will not be required to complete the 3-month in-person visit.

5.3 Procedures for handling subjects incorrectly enrolled or randomized on investigational product

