6.2 Data collection at enrollment and follow-up

Data collection commences after the subject has provided informed consent and has been enrolled in the study. Data collection, including subject demographic information, laboratory tests, and procedural data as well as follow-up visits or telephone contacts will be conducted

Clinical Study Protocol *TWILIGHT Study*
Drug Substance *Ticagrelor & Aspirin*
Study Number *ISSBRIL0345*
Edition Number *Version 4.0*
Date *28-Mar-2016*

by an Investigator or site coordinator who has been trained on the protocol and electronic Case Report Forms (eCRFs).

Data required for analysis will be obtained as outlined in Table 1. After discharge from the hospital, each enrolled subject will be followed with a phone call at 1 month post enrollment and an in-clinic visit at 3 months post enrollment. Enrolled subjects who do not meet eligibility for randomization *prior to* the in-person 3-month visit will not be required to complete the 3-month in-person visit. Subjects who are randomized at 3 months post enrollment will be followed with a phone call at 4 months post enrollment and will return for additional in-clinic visits at 9 and 15 months post enrollment. A final follow-up phone call will be performed at 18 months post enrollment for randomized subjects. No further follow-up contact will be performed for subjects who did not meet eligibility for randomization at the 3 month visit; however, vital status may be obtained from medical or public records at 18 months post enrollment. A flow chart listing the planned visits and their timing can be found in appendix C).

Table 1 Schedule of Data Collection

Type of Data to be Collected	Enrollment	Post-Procedure or Discharge	1 Month (30d) (±7 days) Phone Call	3 Month (90d) (±14 days) Office Visit	4 Month (120d) (±7 days) Phone Call randomized	9 Month (270d) (± 30 days) Office Visit randomized	15 Month (450d) (± 30 days) Office Visit randomized	18 Month (540d) (± 14 days) Phone Call randomized
Eligibility Criteria	X			X				
Patient Informed Consent	X							
Physical Assessment	X							
Medical History/Risk Factors	X							
Cardiac Status	X							
Medications/Antiplatelets	X							
Clinical Tests* Lab tests, ECG	X			X		X	X	
Procedure Information	X							
DAPT Medication Status		X	X		X			X
Angina Status				X	X	X	X	X
Randomization–if eligible				X				
Dispense medication according to EDC		X		X		X		
Randomized Medications – reconciliation of provided medication						X	X	

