6.2.3 In-person follow-up procedure at 9 and 15 months (for randomized subjects)

- Assess for adverse events including MI, unstable angina, stroke, and bleeding.
- Review concomitant medications with subject
- Collect pill bottles, perform study medication accountability, and remind subject about importance of study drug compliance.
- Dispense study medication for next 6 months for those patients still taking study provided medications at the 9-month in-person visit. Patients who have permanently stopped study-provided medications prior to the 9-month in-person visit will continue to be followed but will not be provided additional study medication.
- Instruct the subject to notify the investigator of any occurrence of any adverse events.
- Schedule next clinic visit at 15 months
- Instruct patients to return all study-provided medication at next in-person clinic visit (only pertains to 9-month in-person clinic visit)

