12.1.2 Safety analysis set

Analyses for the primary ischemic endpoint will be performed on the PP cohort. A secondary analysis for the primary ischemic endpoint will be performed in the ITT cohort.

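### The per-protocol compliance rule counts against tablets dispensed, so a patient who stops for good shortly before the 9-month visit stays in the non-inferiority set after more than half the year off study drug

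*Combined protocol and SAP*

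**What the plan says.** Section 12.1 lists two deviations that exclude a randomized subject from the PP set. One is "Subjects not receiving the assigned treatment as allocated by the EDC or no treatment at all". The other is non-compliance with the blinded tablet or ticagrelor: "Non-compliance is defined as taking less than 80% of dispensed tablets based on manual pill bottle count at each study visit". Stopping treatment early is not listed as such.

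Section 12.1.2 gives this set its weight: "Analyses for the primary ischemic endpoint will be performed on the PP cohort". The ITT analysis of that endpoint is secondary.

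Supplies come in two lots. At randomization the site "will provide a 6-month supply of blinded investigational product (aspirin or matching placebo) and open-label ticagrelor" (section 5.2.1). At the second visit the instruction is "Dispense study medication for next 6 months for those patients still taking study provided medications at the 9-month in-person visit" (section 6.2.3). Patients who stopped permanently "prior to the 9-month in-person visit will continue to be followed but will not be provided additional study medication". Section 5.8 agrees: after permanent discontinuation of either study medication, study supply ends and follow-up continues to the end of the study.

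Pill counts are made at the 9- and 15-month visits (section 5.7). The schedule in section 6.2 allows ±14 days at 3 months and ±30 days at 9 and 15 months.

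**The concern.** A compliance ratio for a PP set should fall as time off assigned treatment rises. Here the denominator is what was handed out, and a permanent stop before 9 months prevents the second lot from being handed out. The stop therefore shrinks the denominator as well as the numerator, and a patient with less exposure can pass while one with more exposure fails.

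The PP set is primary for non-inferiority because untreated time makes the arms alike. A control patient who no longer takes blinded aspirin, and a monotherapy patient who no longer takes placebo, differ little in assigned treatment. Keeping them pulls the risk difference toward zero, which favors non-inferiority.

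**Working it through.** The plan gives no compliance figure of its own to reproduce, so the rule is applied directly.

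**Inputs.** One blinded tablet daily (section 5.5.1); threshold 80% of tablets dispensed (12.1); endpoint horizon 365 days from randomization (12.2); visit windows from the schedule in 6.2. Assumption: 180 tablets per 6-month lot, with a range of 168 to 210. At nominal visit days the 9-month visit falls 270 − 90 = 180 days after randomization.

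**Patients who stop before the 9-month visit.** Score = tablets taken / 180, because no second lot exists. The pass mark is 0.80 × 180 = 144 tablets.

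| Last day on drug | Dispensed | Score under 12.1 | Days off, of 365 | In PP set? |
|---|---|---|---|---|
| 143 | 180 | 143/180 = 79.4% | 222 (60.8%) | no |
| 144 | 180 | 144/180 = 80.0% | 221 (60.5%) | yes |
| 179 | 180 | 179/180 = 99.4% | 186 (51.0%) | yes |
| 200 | 360 | second lot 20/180 = 11.1%; pooled 200/360 = 55.6% | 165 (45.2%) | no |

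The order is wrong: the day-200 patient had more treatment than the day-144 patient and is the one removed. Pooling does not change the rows above day 200, because the second lot contributes 0 of 0.

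**Sensitivity to lot size.** With 168 tablets the pass mark is 134.4, so the earliest retained stop is day 135, with 230 days off (63.0%). With 210 tablets it is day 168, with 197 days off (54.0%). Any stop before the nominal 9-month visit leaves more than half the year untreated.

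**Fully adherent patients at the window edges.** Randomization falls on days 76 to 104, the 9-month visit on days 240 to 300, and the 15-month visit on days 420 to 480. The shortest intervals are 240 − 104 = 136 and 420 − 300 = 120 days.
- Separate ratio at each visit: 136/180 = 75.6% and 120/180 = 66.7%; both fail.
- Pooled ratio: the lowest score for an adherent patient is (180 + 120)/360 = 83.3%, when a long first interval exhausts the first lot and a 120-day interval follows. None fail.

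Share of adherent patients with an interval under 144 days, on the separate reading:
- visit days uniform over the windows: about 10% (about 2% at 9 months, 8% at 15 months);
- normal about the target day, SD 7 days at 3 months and 15 days later, clipped to the windows: about 4%;
- SD 5 and 10 days: about 0.5%.

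**Scale of the bias (illustration only).** Days 144 to 179 are 36 of 365 days. Suppose stops are spread evenly over the year and total 4% of patients, borrowing the non-compliance/cross-over rate of section 12.3. Then 0.04 × 36/365 = 0.39%, about 32 of 8200, fall in this window. Their mean time off drug is (365 − 161.5)/365 = 56%. If the true difference equaled the 1.6-point margin and vanished after stopping, the estimate would shift by 0.0039 × 0.56 × 1.6 = 0.0035 points. With 20% stopping it would shift by about 0.018 points.

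**The case against.** The strongest reply is that few patients are affected. Earlier stoppers fail the count and are removed, and the window is about five weeks wide. Under the illustration above the shift is a small fraction of the margin. This stands: a reader might infer that the rule makes the non-inferiority test materially too easy, but the documents give no stopping rates by time or arm and do not support that.

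A reader might also infer that the rule removes perfectly adherent patients as a matter of course. That needs a separate ratio at each visit, with one failure enough to exclude. Section 12.1 says the count is made at each visit but not how the two counts combine. If they are pooled, or if both must fail, no adherent patient is removed with 180-tablet lots. At nominal visit days the score is 100%. What stands is the ambiguity and its conditional consequence.

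A third inference is that the rule misclassifies patients whose visit interval outruns their supply (up to 224 and 240 days against 180 tablets). A patient who takes every tablet and then runs out does score 100%, but that is a matter of supply and visit windows. A days-based denominator would keep such patients too: with intervals of 136 and 240 days, 316/365 = 86.6%.

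Finally, the exclusion for receiving no treatment at all might be thought to cover the stoppers. As worded, it describes patients who never received treatment, not those who took five months of it.

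**Conclusion.** The defect is real and follows from sections 12.1, 6.2.3 and 5.8 read together, on either way of combining the counts. Patients who stop permanently on about days 144 to 179 remain in the set that decides ischemic non-inferiority with 39% to 49% of the year on study drug. The exact days rest on 180 tablets per lot and nominal visit timing; the more-than-half result holds for lots of 168 to 210 tablets. Removal of adherent patients is conditional on the separate-visit reading. The direction of bias is toward non-inferiority. Its size cannot be determined from the documents and is probably small. The definition should be corrected, but the point does not by itself call the non-inferiority conclusion into question.

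**What to change.** In section 12.1, define compliance as tablets taken divided by tablets due under the protocol regimen: one blinded tablet and two ticagrelor tablets per day (assuming one tablet per ticagrelor dose). Pool it from randomization to the earliest of first primary ischemic event, death, withdrawal or last contact, the 15-month visit, or day 365. Keep the 80% threshold. Days after a permanent stop count as due and not taken. The day-144 and day-179 patients then score 144/365 = 39% and 179/365 = 49% and leave the set. An adherent patient with short visit intervals scores 100% and stays.

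The cut-offs are needed so that event cases and censored patients are not failed for tablets that they could not have taken. On a dispensed-tablet count, an adherent patient who dies on day 60 has taken 60/180 = 33%. Where no pill count exists at the cut-off, use the interruption and stop dates that section 5.8 already requires in the EDC.

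The cost is one revised definition and its programming, including some reconstruction from dates; no visit, dose or supply changes. The downside is that more early stoppers leave the PP set. Some will have stopped for bleeding, which the trial expects to differ by arm, so the exclusions may be unbalanced and the ITT analysis should be read alongside. The change does not address gaps caused by visit intervals longer than the supply.
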